2. SYNOPSIS

Please state why this study is not considered a Clinical Trial of an Investigative Medicinal Product	This study is not a clinical trial as we are not investigating the efficacy of prucalopride, but rather using it as a probe to understand the role of 5-HT4 receptors in emotional processing. This study does not fit the MHRA definition of a clinical trial as one designed to: discover or verify/compare a drug's clinical effects; to discover or verify/compare its pharmacological effects (e.g. pharmacodynamics); to identify or verify/compare its adverse reactions; or to study its absorption, distribution, metabolism or excretion (https://www.gov.uk/government/uploads/system/uploads/attachment_data/file/31795 2/Algothrim.pdf)	
List all sites where study will be conducted	Department of Psychiatry, Warneford Hospital, University of Oxford Oxford Centre for Human Brain Activity (OHBA), Warneford Hospital, University of Oxford	
Age Range of Study Participants	18-40 years	
Planned Sample Size	50 healthy volunteers (25 per group)	
Planned Study Duration (n.b. A minimum approval period of 1 year and maximum of 5 years can be granted)	24 months	
Anticipated Start Date	1 st March 2018	
Anticipated End Date	1 st March 2020	
	Objectives	Outcome Measures
Primary	To investigate the effects of seven day prucalopride administration on 1. Recognition of positive and negative facial expressions 2. Performance on Auditory Verbal Learning Task	1. Accuracy (%) and reaction times on computer-based task of facial expression recognition (FERT), comparing those

	(AVLT)	2.	receiving drug and placebo. Number of words correctly recalled across blocks (and number of intrusions and repetitions)
Secondary	To investigate the effects of seven day prucalopride administration: 1. Amygdala response to emotional faces 2. Hippocampal response to novel versus repeated scenes 3. Reward sensitivity 4. Categorisation, recall and recognition of emotional words	1. 2.	in the amygdala during emotional faces task presentation BOLD fMRI signal in hippocampus to pictures of familiar versus novel scenes.
		4.	Number of positive and negative words correctly categorised, recalled, and recognised on emotional memory task

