Work in our group has revealed that short-term treatment with conventional antidepressants such as SSRIs produces positive biases in the processing of emotional information in healthy volunteers (5). For example, seven days treatment with the SSRI citalopram decreased recognition of negative facial expressions and recall of negative vs positive stimuli (6). There is also evidence showing that antidepressants have early effects on neural activity, acting on limbic-cortical brain regions that are known to be dysregulated in depression (7). Indeed, a key study by Godlewska and colleagues from our group showed that 7-day treatment with citalopram reduced activity in the anterior cingulate, insula, amygdala and thalamus in response to fearful versus happy facial expressions. Importantly, depressed patients with the greatest reduction in neural activity across these areas went on to respond better to SSRI treatment (8).

Such effects might be important neuropsychological mechanisms in the mediation of clinical antidepressant action and may also be useful as biomarkers to screen for potential antidepressant activity of novel compounds. It is currently unknown whether activating 5-HT4 receptors has similar effects on emotional

processing and neural activity. Such findings would be consistent with the animal studies and important further demonstration that 5-HT $_4$ receptor agonism might be a potentially useful avenue for antidepressant drug development. A previous study in our group revealed acute prucalopride administration (1mg) in 40 healthy volunteers potentiated learning and memory, whereby significantly more words were remembered in a test of auditory verbal learning and memory, and fewer false alarms were made in a delayed emotional recall task relative to placebo. A single dose of prucalopride did not, however, positively bias emotional processing.

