9. STATISTICS AND ANALYSIS

Do you have a statistical plan?	Yes X	No 🗌
If no, please justify.		
The IBM SPSS statistical software will be use to analyse all behavioural data.		
Demographic and baseline measures will be analysed using independent t-tests.		
Mood, anxiety, and side effect measures will be analysed using repeated measures analysis of variance (ANOVA).		
Behavioural task results will be analysed using between-groups analysis of variance (ANOVA).		
Any significant interactions will be followed up using simple main effect analyses. When assumptions of equality of variances are not fulfilled, the Greenhouse-Geisser procedure will be used to correct the degrees o freedom.		
Analysis of fMRI endpoints will be completed using the FSL software package.		
Number of Participants		
50 healthy volunteers (25 per group)		

Have you done a sample size calculation?	Yes 🖂	No 🗌
If yes, please give details below		
If no, please give details to indicate you have considered the implications the selected		
sample size will have on the study outcome		
We will be using the Emotion Test Battery, which is a well validated set of emotional proces sensitive to antidepressant effects. On the facial expression recognition task, one of the magnitudes is accuracy at recognising fearful facial expressions and a sample size of 25/group power to detect changes of the magnitude of those we have seen in a previous antidepres volunteer study [drug mean 10.64 (SD 9.77) vs. placebo mean 3.36 (SD 5.96) from Harmer Psych; ref 6].	nain outcom would give sant healthy	e e 0.9 y
Analysis of Outcome Measures		
Data analysis will take place at the University of Oxford, Department of Psychiatry and will be undertaken by the research team under the supervision of the Principal Investigator. All data will be analysed using a between-groups analysis of variance (ANOVA). Analysis of fMRI endpoints will be completed using the FSL software package.		·

Withdrawn participants' data will not be included in the analysis.

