4.5 Determination of Sample Size

We will be using the Emotional Test Battery, which is a well validated set of emotional processing tasks that are sensitive to antidepressant effects. On the facial expression recognition task (FERT), one of the main outcome variables is accuracy at recognising fearful facial expressions and this is the variable used for power calculations. Based on data acquired in (Harmer et al., 2004) comparing citalopram to placebo, if we aim for 0.9 power and a 0.05 false positive rate, a suggested total sample size is 38 (G*power) to ensure determination of group level differences at this variable if they exist. As 5HT₄ agonism is less well studied and the dose required of prucalopride for optimal agonism at the receptor is uncertain, we will aim for 25 individuals per group (total sample size of 50).

5. Changes in the Conduct of the Study or Planned Analyses

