6.2 Objectives and Endpoints

These outcomes have been pre-registered on clinicaltrials.gov (NCT03572790). Primary outcomes are identified by bold typeface.

Objectives		Outcome measures / endpoints		
_	ate the effects of seven day e administration compared to			
Primary	Recognition of positive and negative facial expressions	Accuracy to recognise computer-based positive and negative facial expressions (anger, disgust, fear, happy, sad, surprise)		
		Misclassifications (number of responses to each facial expression category incorrectly classified as another facial expression category)		
		Reaction time to recognise facial expressions		
	Performance on Auditory Verbal Learning Task (AVLT)	Accuracy on AVLT (number of items correctly recalled across trials)		
		Number of intrusions (words incorrectly recalled) and number of repetitions (words repeated within the same trial)		
		Number of hits and false alarms in the delayed recognition test		
Secondary	Neural response to emotional faces	Blood Oxygen Level Dependent (BOLD) signal in areas including the amygdala, anterior cingulate cortex, and orbitofrontal cortex		
	Neural response to novel vs. repeated scenes	Blood Oxygen Level Dependent (BOLD) signal to scenes that have previously been seen compared to novel scenes in areas including the hippocampus and parahippocampal regions		
	Reward sensitivity as measured by the Probabilistic Instrumental Learning Task (PILT)	Amount won, amount lost, and total monetary amount earned Accuracy (correct or incorrect symbol choice) and proportion of group choosing correct symbol per trial		

Categorisation, recall, and recognition of emotional words on emotional memory	Emotional Categorisation Task (ECAT): accuracy and reaction time to classify positive and negative descriptor words
tasks	Emotional Recall Task (EREC): number of words correctly recalled (hits) and number of words incorrectly recalled (false alarms)
	Emotional Recognition Task (EMEM): accuracy and reaction time to correctly recognise positive and negative words (hits), and number of incorrectly recognised words (false alarms)
Vigilance to fearful and happy faces on the Facial Dot Probe Task (FDOT)	Vigilance scores derived from reaction time

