8.4.2.1 Primary outcomes

Facial Expression Recognition Task (FERT):

As in previous work (Harmer et al., 2004, Harmer et al., 2009), data will be analysed using repeated measures analyses of variance (ANOVAs). Group (prucalopride or placebo) will be the between-subject factor, and emotion (6 levels) will be the within-subject factor.

Auditory Verbal Learning Task (AVLT):

The number of correctly recalled words on the following trials will be calculated: List A immediate recall trials 1-5. A repeated measures ANOVA will be used to examine if there is an effect of prucalopride administration on word recall (between subject factor: group; within-subject factors: List A acquisition trial). Independent samples t-tests will be conducted to test if there is a group difference in the number of words accurately recalled after a short or long delay (List A short and long delay trials respectively, and the number of intrusions (incorrect words not present in list) and repetitions (correct words recalled more than once in the same acquisition trial) across List A acquisition trials. Independent samples t-tests will also be used to compare List B immediate recall and delayed recognition performance (number of hits and false alarms) between the groups.

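### AVLT delayed recognition is tested as two separate raw counts, so a change in response caution alone can give significantly fewer false alarms, and no planned AVLT score separates caution from memory

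*SAP*

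**What the plan says.** SAP 8.4.2.1, under the AVLT, plans independent-samples t-tests on "delayed recognition performance (number of hits and false alarms) between the groups". SAP 6.2 lists the matching endpoint in the primary AVLT rows: "Number of hits and false alarms in the delayed recognition test".

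Neither document defines a discrimination index or a bias score for the AVLT, says how the two counts are to be read together, or adjusts for testing both. The only statement on Bonferroni correction (SAP 8.4.2) concerns follow-up of a significant interaction. The table of planned comparisons in 8.4.2.2 covers AVLT recall trials, intrusions and repetitions, but not recognition. For the emotional-word tasks, the SAP at least puts hits and false alarms into one model as a within-subject factor.

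The primary status of the recognition counts is unclear. SAP 6.2 states: "Primary outcomes are identified by bold typeface". The bold type is lost in the text available here. The Protocol synopsis gives the AVLT primary measure as "Number of words correctly recalled across blocks (and number of intrusions and repetitions" and does not name recognition.

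**The concern.** Neither count measures memory alone. A participant who says old less readily makes fewer false alarms and fewer hits with unchanged memory. If prucalopride made people more cautious, the false-alarm test could reach significance and be reported as better recognition memory. The hits test might or might not reach significance in the other direction, and the plan does not say what would then be concluded.

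A true gain in recognition memory is also spread over two noisier tests. Each has its own 5% error rate, and there is no single test on which a recognition claim rests.

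**Working it through.** **The plan's own figure.** The only power statement with inputs is for fear accuracy on the FERT (Protocol section 9): "drug mean 10.64 (SD 9.77) vs. placebo mean 3.36 (SD 5.96". The difference is 10.64 − 3.36 = 7.28. The pooled SD is √[(9.77² + 5.96²)/2] = 8.09, so the standardised effect is 0.90. With 25 per group, two-sided 5% and the normal approximation, 7.28/(8.09 × √(2/25)) − 1.96 = 1.22, which gives power 0.889. The noncentral t gives 0.876. The stated 0.9 is reproduced to within about two points. It says nothing about AVLT recognition, for which no power figure is given.

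**Inputs for recognition.** From the documents: 25 per group ("we will aim for 25 individuals per group (total sample size of 50", SAP 4.5), t-tests on the two counts, and a 5% level (two-sided assumed). Not in the documents, hence assumed: 15 targets; 15–30 lures; mean d' 2–3; between-person SD 0.5 for d' and 0.25–0.5 for criterion; equal-variance signal detection with binomial counts.

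**Formulas.** Hit rate = Φ(d'/2 − c). False-alarm rate = Φ(−d'/2 − c). Hence d' = z(hit rate) − z(false-alarm rate), and c = −[z(hit rate) + z(false-alarm rate)]/2.

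**One person, by hand.** Take d' = 2.5.

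| | c = 0 | c = 0.3 |
|---|---|---|
| Hit rate | Φ(1.25) = 0.894 | Φ(0.95) = 0.829 |
| False-alarm rate | Φ(−1.25) = 0.106 | Φ(−1.55) = 0.061 |
| Hits of 15 | 13.4 | 12.4 |
| False alarms of 30 | 3.2 | 1.8 |
| d' | 1.25 + 1.25 = 2.5 | 0.95 + 1.55 = 2.5 |

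False alarms fall by over 40% with memory unchanged.

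**Caution-only effect, simulated** (several thousand trials per setting; range over the settings):

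| Result | Shift 0.2 | Shift 0.3 |
|---|---|---|
| Significantly fewer false alarms | 13–32% | 24–61% |
| The same, without significantly fewer hits | 10–23% | 14–29% |

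At a shift of 0.3 the d' test rejects in 4–6%, its nominal rate. Both counts were significant in the favourable direction in 0% of trials.

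**True memory gain, d' +0.5.** Power is 17–35% for hits alone, 19–45% for false alarms alone, and 42–65% for d'. Within a setting, one count has roughly a third to two thirds of the power of d'. Under the plan either count may be significant: 35–63%, or about 70–98% of the power of d'. The price is type I error. Two independent 5% tests give 1 − 0.95² = 9.75%, and the simulated rate is about 9–11%. Monte Carlo error moves the ends of these ranges by one or two points.

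**Wider assumptions** (288 scenarios; d' gain 0.3–1.2, SD of d' 0.3–0.8, SD of criterion 0.1–0.6). Median power relative to d' is 0.68 for hits (0.28–1.00), 0.61 for false alarms (0.26–1.00), and 0.99 for either count unadjusted (0.52–1.37).

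**The case against.** The strongest reply is that the artefact shows in the planned output. Hits are tested beside false alarms and fall with the same shift, and SAP 8.4 tabulates the means of key endpoints. A careful reader would see both counts drop. This stands in part: it limits the harm. It does not remove it, because in 14–29% of trials at a shift of 0.3 the hits test gives no significant warning, and the plan has no rule for combining the two.

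It is also fair that hits and false alarms are legitimate registered endpoints, and that a pre-stated rule for joint interpretation would close much of the gap.

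Four stronger readings are tempting, and the documents do not support them.

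- *The plan halves the power for recognition memory.* That compares one count with d'. The plan tests both, unadjusted, and recovers most of the power. The cost is mainly type I error.
- *A primary result is at stake.* The counts sit in the primary block, but their own status cannot be confirmed, and the Protocol's primary AVLT measure omits recognition.
- *The investigators already read false alarms this way.* Protocol section 4 does report "and fewer false alarms were made in a delayed emotional recall task relative to placebo" as part of the evidence for better learning and memory. But that was an emotional recall task, where false alarms are wrongly recalled words rather than old/new judgements, and it was cited together with more words remembered. It is indirect support only.
- *The drug will cause caution through fatigue.* Fatigue is a listed side effect, but the Protocol synopsis says reported side effects were no more frequent than on placebo after a single 1 mg dose. A caution effect is a possibility, not a forecast.

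**Conclusion.** The point holds as a gap in scoring and interpretation. AVLT recognition is analysed by two unadjusted tests on raw counts, neither of which isolates memory, and nothing planned for the AVLT separates discrimination from bias. Under the assumed values, a caution shift of 0.3 gives a misleading fall in false alarms in 24–61% of trials, against 4–6% for d'. The power loss for a true gain is modest when both counts are tested, with type I error roughly doubled.

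All these sizes rest on list lengths, d' and spreads that the documents do not give, and on an equal-variance signal-detection model. The size of any drug effect on caution is unknown. The List A trials 1–5 recall ANOVA and the delayed-recall tests are untouched. This is a worthwhile and inexpensive improvement, not a threat to the main AVLT result.

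**What to change.** In SAP 8.4.2.1, replace the two recognition t-tests by two t-tests on per-participant scores from the same counts:

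- **Recognition memory (single test):** d' = z(hit rate) − z(false-alarm rate).
- **Response bias:** c = −[z(hit rate) + z(false-alarm rate)]/2.
- **Correction:** log-linear for everyone, adding 0.5 to each count and 1 to each total before forming rates.
- **Reporting:** keep hits and false alarms, the registered endpoints, as descriptive results. Base any statement about recognition memory on d' only.

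Under a caution-only shift of 0.4, d' rejects in 5–8% of simulated trials, while c detects the shift in 60–95%. A plain hit-rate minus false-alarm-rate index is less clean, with 7–13% false results at 0.4 and up to 20% at 0.5, so d' is preferable.

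The cost is a few lines of scoring and SAP text. No new data are needed, and the number of tests stays at two. The downsides are that d' needs the stated correction for perfect or zero rates, and that the change must be disclosed as a dated SAP amendment. If results have already been seen unblinded, it should be labelled a sensitivity analysis.

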8.4.2.2 Secondary outcomes

Probabilistic Instrumental Learning Task (PILT):

In line with previous work (Walsh, Browning, Drevets, Furey, & Harmer, 2018), independent samples t-tests will be used to compare the amount won, the amount lost, and the total monetary amount earned during the task between prucalopride and placebo groups. The proportion of each group (prucalopride/placebo) who choose the correct symbol in the win condition of the PILT (associated with high probability win) and the loss condition (associated with low probability loss) will be calculated, and plotted on a learning curve to determine where learning plateaus. A mixed model ANOVA will be carried out on the proportion of participants choosing the correct symbol over the trials where learning has plateaued (between subjects factor of group [placebo/prucalopride], within subjects factor of condition [win/loss]). Computational analyses will be conducted on the PILT by fitting a reinforcement learning model to participant choice data. Learning rate and decision temperature parameters will be calculated for the win and loss outcomes. Mixed model ANOVAs with within-subjects factor of learning rate or decision temperature parameter, and between-subjects factor of group, will be used to further characterize the effect of the drug on the task, and complement the non-model based analysis (Pulcu & Browning, 2017).

Categorisation, recognition, and recall of emotional words:

Similar to previous work (Harmer et al., 2009), data will be analysed using mixed model analyses of variance (ANOVAs). Group (prucalopride or placebo) is the between-subject factor, and emotion (positive or negative) and recall or recognition accuracy measures (hits or false alarms) are within-subjects factors.

Vigilance to fearful and happy faces (FDOT):

Data will analysed using mixed models analyses of variance (ANOVAs). Group (prucalopride or placebo) is the between subjects factor and emotion (positive or negative) and probe duration (masked or unmasked) are the within subjects factors.

Visual short term memory as measured by the Oxford Memory Test (OMT)

Data will analysed using mixed models analyses of variance (ANOVAs). Group (prucalopride or placebo) is the between subjects factor and trial condition (1 or 3 memory probes) is the within subjects factors. Analyses will be conducted for accuracy and reaction time.

Planned repeated measure ANOVA comparisons:

Task	Within Subject Factors	Number of Levels	Outcomes Used	Critical Contrasts Tested in the Analyses
FERT	Face Emotion	6 (Fear, anger, happy, surprise, disgust, sad)	% Accuracy Reaction time Misclassifications	Face emotion x treatment group
ECAT	Word Valence	2 (Positive, negative)	Accuracy Reaction time	Word Valence x treatment group
EREC	Word Valence Accuracy	2 (Positive, negative) 2 (Hits, false alarms)	Number of words recalled (correctly and incorrectly)	1. Word valence x treatment group 2. Word valence x accuracy x treatment group
EMEM	Word valence Accuracy	2 (Positive, negative) 2 (Hits, false alarms)	Number of words recognised (correctly and incorrectly) Reaction time	1. Word Valence x treatment group 2. Word valence x accuracy x treatment group
FDOT	Face Emotion Probe Duration	2 (Fearful, happy) 2 (Masked, unmasked)	Vigilance scores derived from reaction time	Face emotion x treatment group

				2. Face emotion x probe duration x treatment group
AVLT	/LT Trial 5 (List A acquisition tria 1-5)		Number of words recalled Number of intrusions Number of repetitions	Trial x treatment group
PILT	Trial type	2 (Win, loss)	1.Proportion of people choosing correct symbol	Trial type x treatment group
ОМТ	Trial 2 (1 probe, 3 probes)		 Proportion of correct probe selections Absolute error for probe location Reaction Time Proportion of misbinding errors 	1.Trial condition x treatment group

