4.4 Blinding

This is a double-blind study. Volunteers and investigators performing the assessments, scans and data analysis will remain blind to the identity of the treatment from the time of randomization until database lock and unblinding. The randomisation code will be kept confidential and will only be accessible to research team not involved directly in data collection and analysis prior to unblinding. Urgent unblinding of a particular participant would also occur in the case of emergency in the opinion of medically-trained personnel.

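### The trials scored in one secondary PILT analysis are to be found from learning curves split by treatment group, with no plateau rule or time of fixing, so the type I error of that analysis can rise

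*SAP*

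**What the plan says.** SAP 8.4.2.2 describes the PILT choice analysis in three steps.

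- The quantity is defined by arm: "The proportion of each group (prucalopride/placebo) who choose the correct symbol in the win condition of the PILT", with the same for the loss condition.
- These proportions "will be calculated, and plotted on a learning curve to determine where learning plateaus".
- The test follows: "A mixed model ANOVA will be carried out on the proportion of participants choosing the correct symbol over the trials where learning has plateaued", with group between subjects and win/loss within subjects. The table of planned comparisons names trial type by treatment group as the critical contrast.

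Other places mention the score but add nothing about the window. Section 6.2 lists it as "Accuracy (correct or incorrect symbol choice) and proportion of group choosing correct symbol per trial", and the table of planned comparisons as "1.Proportion of people choosing correct symbol". Neither mentions a plateau. Section 4.4 says that those doing the assessments and the data analysis "will remain blind to the identity of the treatment from the time of randomization until database lock and unblinding". Section 7.2 places data cleaning and a final data inclusion meeting before unblinding, but does not mention the PILT window.

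**The concern.** The window decides which trials enter the test. As written, it is found from the same group-specific curves that display the difference to be tested. If the start of the plateau is open to judgement, it can be placed, even without intent, where the two curves happen to lie far apart. A test on trials picked that way no longer has a 5% false positive rate. A positive finding on this score would then be hard to defend against the charge that the window was chosen to fit.

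The SAP shows elsewhere how to avoid this: for the AVLT it names the trials in advance (List A, trials 1 to 5).

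**Working it through.** **The plan's own figure.** There is none for this analysis. The only power figure with its own inputs is the protocol's 0.9 for fear accuracy on the facial expression task. The pooled SD is √((9.77² + 5.96²)/2) = 8.09, so d = 7.28/8.09 = 0.90. With 25 per group the normal approximation gives Φ(0.90 × √12.5 − 1.96) = Φ(1.22) = 0.89. That agrees with 0.9 but says nothing about the PILT. Only the group size of 25 is carried forward.

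**What the text fixes.**

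| Question | Answer in the SAP |
|---|---|
| Which curves define the plateau? | Proportions by group and by condition (8.4.2.2) |
| Numerical definition of a plateau? | None |
| Trial numbers or minimum length? | None |
| Same trials for both arms? | Not stated |
| When is the window fixed? | Not stated in 4.4, 7.2 or 8.4.2.2 |

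**Why masking does not settle it.** For participant i let D = (proportion correct, win) − (proportion correct, loss) over the window. The interaction test is t = (mean D in one arm − mean D in the other) / √((s₁² + s₂²)/25). Swapping the arm labels changes only the sign of t, and a two-sided test uses |t|. Curves labelled A and B therefore show everything needed to find the window with the largest |t|.

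**Simulation under no drug effect.** From the documents: 25 per group, two conditions, the trial type by group contrast, and a 5% level (taken as two-sided). Assumed, because the documents do not give them:

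- 30, 60 or 90 trials per condition;
- individual learning curves that rise to an asymptote, with between-subject SD of asymptotic skill 0.3 or 1.0 on the simulated scale;
- possible plateau starts between 20% and 70% of the trials;
- each participant's mean accuracy over the window as the unit.

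The mechanical rule starts the window at the first trial in the permitted range where the smoothed curve reaches 95% of its final level. There were 4,000 to 10,000 replicates per scenario. The Monte Carlo SE at 5% is √(0.05 × 0.95/R), which is 0.34 points at R = 4,000 and 0.22 points at R = 10,000.

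| How the window is set | Type I error, range over scenarios |
|---|---|
| Fixed in advance | 4.6% to 5.6% |
| Mechanical rule on the pooled curve | 4.6% to 6.0% |
| Mechanical rule on group-split curves, one common window | 4.4% to 5.8% |
| Mechanical rule, own window per group | 4.6% to 5.8% |
| Mechanical rule, own window per group and condition | 5.4% to 7.7% |
| Most favourable of five starts | 6.8% to 12.4% |
| Most favourable of all starts in the range | 7.3% to 15.0% |

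The 5.4% to 7.7% row spans both tests: 5.4% to 7.4% for the interaction and 5.6% to 7.7% for the group effect.

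**A second model as a check.** Simulated reinforcement learners were given 30 trials per condition, assumed 70/30 contingencies and 4,000 null trials. A window fixed at trials 11 to 30 gives 4.8% for the interaction. The most favourable start between trials 9 and 15 gives 7.7%, and between trials 6 and 21 gives 11.8%.

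**Plausibility.** Five independent looks would give 1 − 0.95⁵ = 22.6%. The simulated values for five starts are well below that, as expected when the windows overlap heavily.

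Splitting the curves by group is therefore not enough to inflate the error. Inflation needs a free choice made with the group difference in view, or unequal windows by group and condition.

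**The case against.** The strongest reply is that the text describes an ordinary procedure: find where learning has levelled off, then score performance after that point. Much of this stands.

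- A reader might infer that the window is judged by eye. The SAP says only that the curve is plotted; it does not exclude a numerical rule. The defect is an unstated method.
- A reader might infer that each arm gets its own window. Nothing says so, and "over the trials where learning has plateaued" reads most naturally as one set of trials. The SAP does not rule out separate windows, but it does not plan them.
- Section 4.4 covers data analysts: "Volunteers and investigators performing the assessments, scans and data analysis will remain blind to the identity of the treatment" until unblinding. If the window is set while that holds, nobody can knowingly favour the drug. The protection is partial, because the size of the gap remains visible and the SAP does not say that the window is set in that period.
- The higher error rates describe an analyst who takes the best of many windows, under trial counts and learning models that the documents do not supply. They are worst cases for the ranges assumed, not predictions.
- The simulations score each participant's accuracy, whereas the SAP words the outcome as a proportion of participants. The figures apply to the per-participant form.

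None of these points supplies the missing rule or the missing time of fixing.

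**Conclusion.** The concern holds as a gap in specification. The scoring window of one secondary PILT analysis comes from group-split curves, with no plateau rule, no common-window rule and no time of fixing, so the type I error of that analysis can rise. Under the assumptions listed, it stays near 5% with a mechanical rule and one common window, and reaches about 7% to 15% if the most favourable start is freely chosen.

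Two stronger readings are tempting. The first is that the error is in fact inflated. The documents do not support it: they do not say how the window is picked, and one plausible reading gives 4.4% to 5.8%. The second is that the whole reward-sensitivity objective is compromised. It is not: the amounts won, lost and earned, the learning rates and the decision temperatures do not use this window. The primary outcomes are also untouched. This is a minor point, worth making because the remedy costs almost nothing.

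**What to change.** Amend the PILT paragraph of SAP 8.4.2.2 as follows.

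1. State the number of trials per condition and a numerical plateau rule, applied to one curve pooled over both arms. Alternatively, fix the window as the last N trials of each block, with N chosen without sight of the group curves.
2. Use the same trials for both arms.
3. Set the window before unblinding and record it at the data inclusion meeting in section 7.2.
4. Name the window in the section 6.2 outcome list and in the table of planned comparisons.
5. Plot curves by group only afterwards, as description.

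In the simulations a window fixed in advance gives 4.6% to 5.6%, and a rule on the pooled curve gives 4.6% to 6.0%. Both are about nominal.

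If unblinding has already taken place, report how and when the window was set, and whether the group curves had been seen. Show the trial type by group result across a range of alternative windows.

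The cost is SAP wording and one plot from data already collected. No extra participants or measurements are needed.
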